### 6.1.2 Secondary Endpoint Hypothesis

The secondary endpoint is intended to demonstrate physician preference for anatomic placement over targeted placement.

#### Hypothesis:

[figure not shown]
The hypothesis is formally addressed as:

$H_0: P \leq 60\%$

$H_1: P > 60\%$

where P= percentage of physician prefer anatomic placement over targeted placement.

#### Analysis

## 6.2 Justification of Clinical Investigation Design

To date, no clinical evidence has been generated for the use of BurstDR during trial evaluation for SCS or for the Invisible Trial System with any stimulation mode. BurstDR used with permanent SCS systems has provided better patient experiences compared to tonic stimulation (e.g., pain relief and satisfaction). The trial system, capable of delivering both BurstDR and tonic stimulation modes, may provide additional benefits by making BurstDR available during the trial evaluation and by providing an alternative stimulation mode if BurstDR fails. Furthermore, the Invisible Trial System provides a streamlined, wire-free trial experience for subjects, and establishing subject impressions of the system are integral to the marketing of this improved system.

The primary aim of this clinical investigation is to establish that anatomic lead placement for BurstDR trials results in non-inferior qualification rates compared to the traditional targeted lead placement technique. The ability to anatomically place trial leads is potentially important because it should reduce procedure time, which benefits both physicians and patients. Prior to the availability of BurstDR stimulation, anatomic placement was not indicated due to the sensory experiences of tonic stimulation. Thus, the current clinical investigation will establish the feasibility of the anatomic placement procedure. Additionally, establishing the physician's preference of anatomic placement and the effect of anatomic placement on procedure time will inform clinical care. Thus, the chosen endpoints capture qualification rate, physician preference, procedure time, and descriptive information. All of these are designed to explore procedure benefits, clinical experience, and patient experience.

To limit knowledge bias, this clinical investigation will be single blinded (i.e., subjects will not be made aware of the group to which they are randomized). Additionally, a standardized script will be provided to study site personnel to assist with patient interaction as a way to minimize the risk of disclosing randomization assignments.

The primary marker of success during the typical SCS trial evaluation period is qualification for permanent implant. Qualification per standard of care for SCS devices includes a successful trial evaluation period defined by subject's assessment of 50% or more pain relief during the trial evaluation, physician's recommendation, and the subject's willingness to continue to the permanent system. As such, the current clinical investigation defines qualification for permanent implant as a composite endpoint based upon standard of care to be used as for the primary endpoint. Demonstration of non-inferiority will establish that the anatomic placement technique is similar to traditional, targeted techniques in terms of subject selection for permanent implant. Secondary and descriptive endpoints will provide evidence of the physician and patient experience with both types of implant procedures and with the Invisible Trial System, overall.

As the primary hypothesis will be tested prior to actual permanent implant status, the clinical investigation will end at the qualification stage without consideration of the actual permanent implant status for subjects. Qualification based on efficacy, subject self-selection, and physician discretion is sufficient to make inferences about the anatomic procedure and Invisible Trial System features.

Failure to qualify for this study is contingent upon a minimum of 5 days of stimulation. Anecdotal reports indicated that burst stimulation may take up to 5 days to impart full benefit; whereas, tonic stimulation does not historically have a wash-in period to reach full benefit. As such, failures occurring before 5 days may be a product of insufficient exposure to burst therapy, and the primary endpoint is contingent upon equitable treatment between randomization arms in all other aspects excepting procedure. Additionally, subjects who fail the burst trial and proceed to an extended trial evaluation with tonic stimulation will need to ensure that they are provided sufficient time to assess the alternate stimulation mode. At present, the wash-out period for burst, if any, has not been established but is suspected to be at least a few hours and up to 2 days. As such, subject's ending their trial evaluation before 5 days without meeting criteria for qualification for permanent implant will be considered a deviation and treated as missing data. Use of this criterion will also

allow exploratory analyses for potential wash-in and wash-out periods for burst stimulation, that are yet to be established in a clinical study.

### **6.3 Multiplicity**

There is one primary endpoint and one secondary endpoint of this clinical investigation. The secondary endpoint will be tested when the primary endpoint is met. Therefore, no multiplicity adjustment is needed.

### **6.4 Overall Sample Size**

### **6.5 Descriptive Endpoints**

Descriptive endpoints are reported using only summary statistics and no hypothesis tests will be performed.

1. Overall procedure time (in-room to out-room), implant procedure time (needle-in to needle-out), and total time of intra-operative fluoroscopy exposure for each randomized group and stratified by number of leads and lead type (permanent lead or temporary lead).
2. Programming time required for each randomized group.
3. Change from pre-implant Numerical Rating Scale (NRS) in each randomized group to end of initial trial evaluation period and to the end of the extended trial evaluation period, as applicable.
4. Number of subjects in each randomized group who have affirmative assessment for each of the independent criteria required for qualification for permanent implant.
5. Proportion of subjects in each randomized group who do not qualify for permanent implant, however do proceed with permanent implant per physician discretion.
6. Time from trial system implant to >50% PRP measured by the number of days (also known as "wash-in period").
7. Rate of serious adverse device effects (SADE) in each group.
8. Number and proportion of meaningful lead migrations\* during the initial trial evaluation periods by treatment group.
9. Number and proportion of meaningful lead migrations\* during the initial trial evaluation period in subjects who have a temporary trial lead implant compared to subjects who have a permanent trial lead implant.
10. Clinician assessment of anesthesia related difficulty (assessed primarily in the procedure room for the trial) on a 5 point likert scale for each randomized group.
11. Clinician assessment of lead placement difficulty on a 5 point likert scale for each randomized group.
12. Clinician affinity (liking) for lead placement technique at the end of the trial implant procedure.
13. Permanent system qualification rate at the end of extended trial period.

\*A meaningful lead migration is defined as a lead migration resulting in the inability to program for therapeutic response

### **6.6 Timing of Analysis**

Analysis will be performed when the last enrolled subject completes the initial trial evaluation or, if subject failed to qualify during the initial trial evaluation period and participated in the extended trial period, after completion of the extended trial period.

## 6.7 Success Criteria

The clinical investigation will be considered a success when the primary endpoint is met.

## 6.8 Interim Analysis

No interim analyses are planned for this study.

## 6.9 Statistical Criteria for Termination

There are no statistical criteria for termination of this clinical investigation.

## 6.10 Deviations from Statistical Plan

If any deviations from the original statistical plan occur, such deviations will be documented in the clinical study report or statistical report containing the analysis results.

# 7 Risks and Benefits

The risks associated with the use of the 'Invisible Trial System' are anticipated to be comparable to those associated with the use of other currently available SCS trial systems. Subjects participating in this study are indicated for an SCS trial neuromodulation system as part of their standard medical management and are subject to the risk associated with the use of these devices. The study does not require any additional procedures or assessments over the standard of care.

This study may or may not benefit the subjects involved, but may help future subjects by increasing current knowledge and understanding of treatment options for subjects who are indicated for the trial neuromodulation system for SCS.

Lead placement for BurstDR™ has proceeded to use temporary tonic stimulation such that the sensory qualities of tonic programming (paresthesias) can be used to elicit feedback from patients and ensure the leads are properly placed and programmed. Because BurstDR™ results in sensation-free therapy for most patients, it has been proposed that anatomic placement of the leads could result in effective therapy while reducing procedure times during both the trial evaluation and permanent system implants. This benefit may be applicable for subjects randomized to Group 1 (AB).

## 7.1 Risks Associated with the Device Under Investigation

There are no additional risks to the study subjects beyond those associated with the implant and use of the approved trial neuromodulation systems. Please refer to section 7.1.1 for the list of anticipated adverse events.

### 7.1.1 Anticipated Adverse Device Effects

The implantation of a SCS trial system is an invasive procedure and therefore carries certain risks. In addition to those risks commonly associated with surgery, the following anticipated adverse device effects are associated with implanting or using the trial neuromodulation system for SCS:

- Unpleasant sensations or motor disturbances, including involuntary movement, caused by stimulation at high outputs (If either occurs, turn off the EPG immediately.)
- Undesirable changes in stimulation, which may be related to cellular changes in tissue around the electrodes, changes in electrode position, loose electrical connections, or lead failure
- Stimulation in unwanted places
- Lead migration, causing changes in stimulation or reduced pain relief
- Epidural hemorrhage
- Hematoma
- Infection

- Spinal cord compression
- Paralysis from placement of a lead in the epidural space
- Cerebrospinal fluid (CSF) leakage
- Paralysis
- Weakness, clumsiness, numbness, or pain below the level of the implant
- Allergic or rejection response to implant materials
- Seroma (mass or swelling) at the implant site
- Local skin erosion
- Persistent pain at lead site

### 7.1.2 Risks Associated with Clinical Investigation Assessments

The risks involved with this clinical investigation are comparable to those associated with the implant of any other commercially available neuromodulation system.

## 7.2 Risk Control Measures

Every possible effort will be taken to minimize the risks, including:

- Careful selection of experienced Investigators for the clinical investigation
- Adequate monitoring for each clinical investigation site
- Conducting the clinical investigation in accordance with the CIP, all applicable laws and regulations and any conditions of approval imposed by the appropriate IRB/EC or applicable regulatory authorities where the clinical investigation is performed
- Training of Investigators both on the CIP, lead placement procedure, anchoring technique and imaging guidelines.

## 7.3 Possible interactions with concomitant treatments

There are no known interactions of the neuromodulation trial system with concomitant medical treatment or with any previously implanted active devices. Please refer to the Clinician's Manual for the SJM™ External Pulse Generator and leads for information related to MRI compatibility.

## 7.4 Risk-to-Benefit Rationale

Any undesirable side effects, under normal conditions of use, are considered to be acceptable risks when weighed against the performance of the device and benefits to the subject.

# 8 Requirements for Investigator Records and Reports

## 8.1 Deviations from CIP

A deviation is defined as an instance(s) of failure to follow, intentionally or unintentionally, the requirements of the CIP. The investigator should not deviate from the CIP.

In some cases, failure to comply with the CIP may be considered failure to protect the rights, safety and well-being of subjects; such non-compliance exposes subjects to unreasonable risks. Examples: failure to adhere to the inclusion/exclusion criteria, failure to perform safety assessments intended to detect adverse events. Investigators should seek to minimize such risks by adhering to the CIP.

The PI must maintain accurate, complete, and current records, including documents showing the date of and reason for each deviation from the CIP. Relevant information for each deviation will be documented as soon as possible on the applicable CRF. The site will submit the CRF to the Sponsor.

The PI is required to adhere to local regulatory requirements for reporting deviations to IRB/EC.

Under emergency circumstances, deviations from the CIP to protect the rights, safety and well-being of subjects may proceed without prior approval of the Sponsor and the IRB/EC. Such deviations shall be documented and reported to the Sponsor and the IRB/EC as soon as possible.

## 8.2 Safety Reporting

Safety surveillance and safety reporting by the investigator starts as soon as the subject is enrolled in this clinical investigation (date of signature of informed consent).

The safety surveillance and the safety reporting will continue until the last investigational visit has been performed, the subject is deceased, the subject/investigator concludes his participation into the clinical investigation or the subject withdrawal from the clinical investigation.

Per this CIP, the applicable reportable adverse events data including deaths will be collected throughout the clinical investigation and will be reported to the Sponsor through the EDC system. The Sponsor will ensure that all applicable events are reported to the relevant authorities as per regulations. The investigators must notify the IRB/EC, if appropriate, in accordance with their institutional requirements, national and local laws and regulations, of the AEs reported to the Sponsor.

Adverse events will be monitored until they are adequately resolved or the subject has ended his/her participation in the clinical investigation, whichever comes first. The status of the subject's condition should be documented at each visit.

Descriptive endpoints for the safety datapoints are as follows:

1. Rate of serious adverse device effects (SADE) in each group.
2. Number and proportion of meaningful lead migrations\* during the initial trial evaluation periods by treatment group
3. Number and proportion of meaningful lead migrations\* during the initial trial evaluation periods in subjects who have a temporary trial lead implant compared to subjects who have a permanent trial lead implant.

\*A meaningful lead migration is defined as a lead migration resulting in the inability to program for therapeutic response

For the purposes of this clinical investigation, the following events will be reported:

- All Adverse Device Effects (non-serious device/procedure related)
- All Serious Adverse Events (whether or not the event is considered device/procedure related)

Reportable adverse events shall be submitted to the Sponsor as soon as possible after becoming aware of the event. The sites should notify the Sponsor of reportable adverse events by creating and saving the applicable CRF within the electronic data capture (EDC) system. Additional information may be requested by the Sponsor in order to support the reporting of AEs to regulatory authorities. All adverse events will be reported as per applicable regulatory requirements.

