**Postoperative Programming:**

After the trial system implant procedure is complete, all subjects will be programmed with BurstDR™ stimulation programs by trained personnel and/or an Abbott representative using the Clinician Programmer. Subjects will be given a Patient Controller and instructed how to use the Patient Controller to adjust stimulation as needed to produce the best results and to complete the Patient Trial Diary daily during the trial evaluation period

During the initial trial evaluation period, the stimulation parameters may be optimized. If this is needed, the subject would return to the clinic for adjustments to the programming parameters. Study personnel performing programming activities will utilize the same methods as the post-op programming to ensure the subject remains blinded to treatment group. This visit should be documented as an unscheduled visit. If a lead revision is needed during the trial period, the subject should be withdrawn from the study.

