## **5.10 Subject Withdrawal**

Subjects must be informed about their right to withdraw from the clinical investigation at any time and for any reason without sanction, penalty or loss of benefits to which the subject is otherwise entitled. Withdrawal from the clinical investigation will not jeopardize their future medical care or relationship with the investigator. Subjects will be requested to specify the reason for the request to withdraw. The investigator must make all reasonable efforts to retain the subject in the clinical investigation until completion of the clinical investigation.

Examples of reasons for subject’s withdrawal include, but are not limited to:

- Subject and/or family request to withdraw consent
- Subject death
- Unsuccessful trial implant resulting in ineffective stimulation
- Lead revision
- System explant

The status of the subject’s condition should be documented at the time of withdrawal.

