#### Serious Adverse Event (SAE)

An adverse event that led to:

- Death
- A serious deterioration in the health of the subject, that either resulted in:
  - A life-threatening illness or injury OR
  - A permanent impairment to a body structure or a body function OR
  - An in-patient or prolonged hospitalization OR
  - A medical or surgical intervention to prevent life-threatening illness or injury or permanent impairment to a body structure or a body function OR
  - A malignant tumor (only for specific countries)
- Fetal distress, fetal death or a congenital abnormality or birth defect

A planned hospitalization for a pre-existing condition, or a procedure required by the CIP is not considered a serious adverse event.

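### Follow-up of an open adverse event stops at study exit or withdrawal, so final outcome, later seriousness and late complications can be missed in the SADE rate

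*Combined protocol and SAP*

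**What the plan says.** Section 8.2 contains two stopping rules.

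- **Surveillance of the subject.** It runs from consent until the last visit or death, or until "the subject/investigator concludes his participation into the clinical investigation or the subject withdrawal from the clinical investigation".
- **Monitoring of an individual event.** It runs "until they are adequately resolved or the subject has ended his/her participation in the clinical investigation, whichever comes first". The closing phrase belongs to this sentence only.

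Other sections decide when participation ends.

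- Section 5.4.3, under Postoperative Programming: "If a lead revision is needed during the trial period, the subject should be withdrawn from the study".
- Section 5.10 lists examples of reasons for withdrawal. They include "Lead revision", "System explant" and an implant that does not give effective stimulation. They stand beside withdrawal of consent, with no distinction for safety data.
- Section 5.4.4: the initial trial period lasts at least 3 days, and a subject who qualifies then leaves the study.

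The plan does capture events up to that point. All ADEs and all SAEs are reportable, and section 8.2 adds: "Reportable adverse events shall be submitted to the Sponsor as soon as possible after becoming aware of the event". Section 5.10 asks that the subject's "condition should be documented at the time of withdrawal". Sections 4.3.3, 6.5 and 8.2 name the rate of SADEs in each group as a descriptive endpoint.

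**The concern.** Whether an event counts as serious can depend on what happens after onset. Appendix B includes hospitalization, prolonged hospitalization, certain interventions, and "A permanent impairment to a body structure or a body function". An infection that is a non-serious ADE on the day the subject leaves may lead to hospitalization later. Under section 8.2 as written, nobody has to find that out or update the record.

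The SADE rate is the plan's only rate of serious device harm by group. Section 7.1.1 names infection, epidural hemorrhage and CSF leakage among the anticipated effects. The plan also ties some device problems to leaving the study, so follow-up can end at the point where an event still needs watching. A revision or explant can have complications of its own, and these fall after the cut-off whenever the subject is withdrawn for it.

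**Working it through.** The documents state no expected rate of SADEs, lead revisions, explants or withdrawals, so there is no plan figure to reproduce. The check is a comparison of the text, followed by an illustration of scale.

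**Step 1. Is there any follow-up after exit?** Section 8.2 ends event monitoring at the end of participation even if the event is unresolved. Section 5 asks the principal investigator to arrange care after completion, which is care and not data collection. Section 8.2 lets the sponsor request more information to support regulatory reporting, which is an option and not a follow-up rule. No section sets a contact or record check after exit.

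**Step 2. Which subjects does this reach?**

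| Route out of the study | Source | What the text does |
|---|---|---|
| Lead revision | 5.4.3 and 5.10 | Withdrawal directed in 5.4.3, example reason in 5.10 |
| System explant | 5.10 | Example reason only |
| Ineffective implant | 5.10 | Example reason only |
| Qualifies | 5.4.4 | Exit after at least 3 days |

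The cut-off therefore applies to every subject who leaves, not only to those withdrawn.

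**Step 3. What is recorded and what is not?** The triggering event and the condition at withdrawal are recorded (8.2 and 5.10). Adverse event forms apply from the implant visit on, including unscheduled visits (Table 2 and 5.5). Three things have no required record: the final outcome of an event still open, a later change to serious, and complications that begin after the subject has left.

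**Step 4. Scale, as an assumption only.** Let p be the true SADE rate, and u the share of true SADEs that first become serious, or first appear, after exit. Then observed rate = (1 − u) × p. Neither p nor u is in the documents. With p assumed at 4%:

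- u = 0: 1.00 × 4% = 4%
- u = 0.25: 0.75 × 4% = 3%
- u = 0.50: 0.50 × 4% = 2%

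For two groups the observed difference is (1 − u₁)p₁ − (1 − u₂)p₂. It equals the true difference when u is zero in both groups, and is generally distorted otherwise. The documents do not allow u to be set for either arm.

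**Step 5. Internal tension.** Section 5.4.3 directs withdrawal after a needed lead revision. Section 5.10 obliges the investigator to make every reasonable effort to keep the subject in until completion. The two need reconciling.

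**The case against.** The strongest reply is that the important facts are already captured. The event behind a revision or explant must be reported promptly, and the subject's condition is documented at withdrawal. Many such events can be classified at once, because Appendix B counts surgical intervention to prevent permanent impairment as serious. The EDC allows later changes with an audit trail (9.2). The case report and consent forms are only headings in the public copy, so how updates are handled is not known. The endpoint is one of 13 descriptive ones with no test, success rests on the primary endpoint alone (6.7), and the devices are market released.

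Most of this stands, and it rules out several stronger readings that a reader might infer.

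- *Subjects with the worst complications are lost before seriousness is known.* The triggering event is reported and can often be graded at withdrawal. Revision or explant is not in itself an SAE under Appendix B.
- *Surveillance always ends on the day of explant.* No section directs withdrawal for explant. It is an example in 5.10, which sets no withdrawal date and asks for retention.
- *A later upgrade can never enter the database.* The absence of required follow-up does not bar an update.
- *The arm with more complications is favoured.* Anatomic leads need no tonic confirmation while targeted leads are adjusted by it, so a difference in revisions is conceivable. The documents give no data on it, and the same cut-off applies to ordinary completers.

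What the reply does not answer is that a report made on the day of exit describes the event as it stood that day. Nothing in the visible plan requires its outcome to be established afterwards.

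**Conclusion.** The point holds in a limited form. Section 8.2 states a rule that stops following an unresolved event when the subject leaves, and no other section makes up for it. Final outcome, later seriousness, and complications of a revision or explant can therefore be missing from the SADE rate by group.

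The size cannot be established. The range of 4, 3 or 2% for a true 4% rests wholly on assumed values of p and u, and a difference between arms is possible but not shown. The primary endpoint and its test are unaffected. This is a low-cost improvement to the ascertainment of a planned safety endpoint, not a flaw that threatens the trial's main conclusion.

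**What to change.** 1. **Section 8.2.** Replace the end-of-participation limit on event monitoring. Any reportable event open at exit or withdrawal is followed through routine records or by phone until it is resolved, stable, or reaches a common cut-off that the sponsor sets for both arms, unless consent is withdrawn. Align the surveillance sentence with this. Record final outcome and seriousness on the existing AE CRF, and count a later upgrade in the SADE rate.
2. **Section 5.10.** Separate leaving the efficacy assessment (lead revision, explant, ineffective implant) from withdrawing consent for safety data. This brings complications of the revision or explant itself within follow-up.
3. **Sections 5.4.3 and 5.10.** Reconcile the directed withdrawal after lead revision with the duty to retain the subject.

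One limit remains: a new event that starts after an ordinary exit with nothing open would still fall outside, and the report should say so.

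The cost is protocol wording, a chart check or phone call for the subjects concerned, a slightly later data lock for a few subjects, and possibly a line in the consent form with the ethics review that this needs. No visit or procedure is added.

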#### Adverse Device Effect (ADE)

An adverse event related to the use of a medical device.

[figure not shown]
This definition includes adverse events resulting from insufficient or inadequate instructions for use, deployment, implantation, installation, or operation, or any malfunction of the medical device.

This definition includes any event resulting from the use error or from intentional misuse of the medical device.

[figure not shown]

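### Safety by arm is limited to serious adverse device effects and meaningful lead migrations, although the arms differ only in the implant procedure

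*Combined protocol and SAP*

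**What the plan says.** Section 8.2 (Safety Reporting) names three descriptive safety endpoints. The first is "Rate of serious adverse device effects (SADE) in each group". The second is the number and proportion of meaningful lead migrations "during the initial trial evaluation periods by treatment group". The third splits the same migrations by temporary or permanent lead, not by arm. The three appear again as items 7 to 9 in sections 4.3.3 and 6.5, where descriptive endpoints are limited to summary statistics without tests.

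The reporting duty on sites is wider. Section 8.2 requires every serious adverse event, related or not. For non-serious events it requires "All Adverse Device Effects (non-serious device/procedure related".

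The terms are defined in Appendix B. An adverse device effect (ADE) is "An adverse event related to the use of a medical device", with an extension that reaches inadequate instructions for deployment and implantation, malfunction and use error. A SADE is an ADE with a serious outcome. Only the general adverse event definition expressly takes in events arising from procedures. Section 7.1.1 begins "In addition to those risks commonly associated with surgery, the following anticipated adverse device effects are associated with implanting or using" the trial system, and its list then includes epidural hemorrhage, hematoma, infection, CSF leakage and paralysis from lead placement.

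On the arms themselves, sections 4.1 and 5.4.3 give both groups the same trial system and BurstDR programming. Section 6.2, in justifying the five-day rule, says that "the primary endpoint is contingent upon equitable treatment between randomization arms in all other aspects excepting procedure".

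**The concern.** The trial compares two ways of placing leads, so the useful safety comparison is the harm that follows each way. The general adverse-event rate planned by arm is instead restricted twice: to serious events, and to events classed as device effects. A non-serious hematoma, infection or CSF leak after placement would be reported by the site but would appear in no planned by-arm table. The same holds for a serious event judged unrelated to the device.

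Section 6.2 expects the results to guide practice on placement technique. A non-inferior qualification rate is harder to interpret without a by-arm account of procedural complications. If the summaries are not fixed in advance, the choice of safety counts to show can also be made after the data are seen.

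A second issue is classification. Whether an event enters the SADE rate depends on a relatedness judgment made under wording that is not uniform. Section 5.4.2 says that implanting physicians and surgical support staff cannot be blinded.

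**Working it through.** No arithmetic applies. The documents state no expected safety event rate and the public copy has no sample-size text, so there is no figure to reproduce. The check sets the reporting duty in section 8.2 against the endpoint lists in 4.3.3, 6.5 and 8.2.

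**Step 1. What is collected, and what is summarized by arm**

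| Type of event | Reported by sites (8.2) | Planned by-arm summary |
|---|---|---|
| Serious, attributed to the device | Yes | Yes, as SADE |
| Serious implant complication of a kind listed in 7.1.1 | Yes | Probably, as SADE |
| Serious, judged due to the procedure or anesthesia but not the device | Yes, as SAE | Unclear; none if the core ADE definition is applied strictly |
| Serious, judged unrelated to device and procedure | Yes, as SAE | None |
| Non-serious, device- or procedure-related | Yes | None, apart from meaningful lead migration |
| Lead migration that prevents therapeutic programming | Yes | Yes, as its own endpoint |

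Two safety endpoints are therefore reported by arm. Two collected categories have no by-arm summary beyond what those endpoints capture: all SAEs, and non-serious device- or procedure-related events.

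**Step 2. Whether procedure-related events count as SADEs**

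- Section 8.2 describes ADEs as related to the device or the procedure, so procedure events are in.
- The core ADE definition in Appendix B mentions only use of the device. Its extension names deployment and implantation, so procedure events are partly in.
- The general adverse event definition in Appendix B includes procedure events explicitly. The ADE and SADE definitions do not repeat this.
- Section 7.1.1 sets ordinary surgical risks apart, then lists implant complications as device effects.

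Read together, these place most serious implant complications inside SADE. They do not settle an event attributed to the procedure or anesthesia alone. Anesthesia is relevant to the comparison, because item 10 of section 4.3.3 has clinicians rate anesthesia-related difficulty for each group.

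**Step 3. Whether the non-serious gap depends on that reading**

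It does not. Even if every implant complication is a device effect, the SADE rate excludes the non-serious ones by definition.

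**Step 4. Denominator**

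Sections 4.3.3, 6.5 and 8.2 do not say which subjects form the denominator of the SADE rate. The population in section 6.1.1.3 would not suit: it takes only randomized subjects classified as qualified or not qualified. Section 5.10 lists unsuccessful trial implant, lead revision and system explant among the reasons for withdrawal, so subjects with a difficult procedure could fall outside it.

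**The case against.** The strongest case on the other side is that the plan already compares a good deal of technique-related harm and burden by arm. Meaningful lead migration directly follows SADE in section 8.2 and is closely tied to lead placement. Section 7.1.1 lists lead migration as an anticipated device effect. Fluoroscopy time, anesthesia-related difficulty and lead placement difficulty are also reported by group. The ADE concept is broad: section 7.1.1 says that "anticipated adverse device effects are associated with implanting or using the trial neuromodulation system for SCS", and epidural hemorrhage and paralysis from lead placement are on its list. The endpoints carry no test, success rests on the primary endpoint alone, and the devices are market-released.

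Most of this stands, and it rules out three stronger readings that a reader might infer:

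- That SADE is the sole adverse-event comparison between arms. Lead migration by treatment group is a second one.
- That SADE counts only events the device itself brings about, so that implant harm is excluded. Section 7.1.1 and the Appendix B extension point the other way for most serious implant complications.
- That technique-related harm would go unrecorded. Section 8.2 requires these events to be reported; what is missing is a prespecified summary by arm.

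A reader might also infer that coding of relatedness will be biased because sites know the allocation. The documents do not say who makes the relatedness judgment, so this is a possibility rather than a finding.

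The objection does not close the gap. Lead migration does not capture bleeding, infection, neurological or anesthetic events. Difficulty ratings and fluoroscopy time measure burden, not adverse events. Nothing in the plan gives a by-arm count of non-serious complications or of all SAEs.

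**Conclusion.** The concern holds as a limit on safety reporting. The by-arm safety endpoints are the SADE rate and meaningful lead migrations. All SAEs, and non-serious device- or procedure-related events, are collected without a planned by-arm summary, and the wording leaves open whether some procedure-related events count as SADEs.

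Its size cannot be put in percentage points, because the documents give no safety event rates. In scope, it affects two collected categories and one definition. The primary hypothesis, its margin and its error rate are untouched.

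The conclusion assumes that the endpoint lists in 4.3.3, 6.5 and 8.2 are complete. Appendix F (case report form) is not shown in this copy, so nothing is concluded about how relatedness is recorded. The change is worth making because the data are already required and the trial compares procedures. A count of all SAEs also needs no relatedness judgment, so it is unaffected by the inconsistent wording.

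**What to change.** Replace item 7 in sections 4.3.3 and 6.5, and the first safety endpoint in section 8.2. Report, by randomized group and among subjects with an attempted or completed trial implant, the number and proportion with:

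- (a) any SAE, regardless of relatedness;
- (b) any SAE related to the device or the procedure, with SADE shown as a subset;
- (c) any non-serious event related to the device or the procedure.

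Keep the lead migration endpoints as they are. Reconcile Appendix B with section 8.2 by stating whether procedure-related events, including those related to anesthesia, count as ADEs and SADEs.

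The cost is wording changes in four places and a few more rows in the safety table. No new category of event has to be collected. The drawback is that the headline adverse-event rate will be higher than the SADE rate alone, which the report should explain.
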